11.4 VACS Index

The VACS Index is a validated biomarker score that reflects overall health and is a potent predictor of mortality in HIV-infected patients [147, 148]. The VACS Index is calculated by summing scores for age, CD4 count, HIV-1 RNA, hemoglobin, liver fibrosis (FIB-4), renal function (eGFR), and HCV status (**Table 11.1**) [148, 149]. It is responsive to abstinence among HIV-infected patients receiving opioid agonist treatment even when they enter such treatment with an undetectable HIV viral load [150]. A clinically meaningful difference is 5 points as it relates to a 20% change in 5-year mortality risk [147-149]. It will be assessed at randomization and week 24, or the end of study visit, if not week 24.

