13.5 Clinical Laboratory Tests

Trained staff will be responsible for collecting and processing biologic specimens. Local laboratories at participating sites will be used to conduct all laboratory tests with the exception of the PBMCs. Laboratories must participate in the Clinical Laboratory Improvement Act of 1998 (CLIA) or be accredited by the College of American Pathologists (CAP). If neither CLIA nor CAP is available, equivalent evidence of laboratory certification may be acceptable and must be discussed on a case-by-case basis with the Lead Team. Laboratories should provide reference ranges and proof of laboratory certification.

HIV-1 RNA PCR: will be drawn at screening, 12, and 24 weeks (or the end of study visit, if not week 24) for outcomes assessment. At screening, results of laboratory tests conducted within 90 days prior to date of informed consent will be acceptable.

CD4 Count (T-helper cells): will be drawn at randomization and at 12 and 24 week visits or the end of study visit, if not week 24, for secondary outcomes assessment. At randomization, results of laboratory tests conducted within 90 days prior to date of informed consent will be acceptable.

Peripheral Blood Mononuclear Cells (PBMCs): For all randomized participants (both TAU and XR-NTX), we will collect four 8mL or eight 4mL CPT tubes for PBMC analysis at randomization,

12, and 24 (or end of study visit if not week 24). Blood draws may coincide with other research blood draws. PBMC analysis will be conducted in a related NIH application to assess the effects of opioid blockade on TLR mediated immune responses at a later time. PBMC samples will be shipped to a lab at Oregon Health & Science University and kept indefinitely. PBMC samples will be used for immunologic testing. It is also possible that banked PBMC specimens will be shared with other investigators for performance of genetic testing in the future.

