The RMVL is a type of longitudinal model. In theory, longitudinal models can accommodate missing data better than non-longitudinal models because they incorporate all non-missing data points. But this approach assumes that missing data are not informative, that is, that missing values are probably similar to corresponding non-missing values with the same set of other predictors. For trials of substance-using individuals, missing at random (MAR) is less likely than missing not at random (MNAR) alternative: if data are missing, it is probably because the participant is unsuppressed. So, for the primary analysis, “unsuppressed” will be substituted for missing suppression status values. An exception is that, if missing data are flanked on both sides by “suppressed” values, we will impute the missing data to be suppressed. Since death is at least

as undesirable as lack of suppression, “unsuppressed” will be assigned as a status value for visits subsequent to death. A secondary sensitivity analysis will explore the extent to which trial conclusions need to be changed as the missingness assumption approaches MAR.

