17.9 Analysis of secondary outcomes

Secondary outcomes will be analyzed as indicated in the italicized text describing each secondary endpoint.

1) Secondary HIV outcomes:

- a. **Change in VACS index** at week 24 compared with randomization (score based on lab measurements). T-test.
- b. **Change in CD4 count** at 24 weeks following randomization compared with randomization (count; laboratory measurement). T-test.

2) Engagement in HIV Care:

- a. **ART prescribed** Change in the proportion of study participants prescribed ART within 24 weeks following randomization, compared to baseline (binary; medical record abstraction). *Each individual can be scored either 0 (not prescribed ART) or 1 (prescribed ART) at both baseline and follow-up, after which his or her outcome score will be the follow-up score minus the baseline score. Outcome scores will be analyzed via rank-based methods such as Wilcoxon rank-sum tests. Covariates can be considered via the cumulative logit model.*
- b. **ART Adherence** Proportion of participants taking 100% of prescribed ART doses in the past month at 24 weeks for those prescribed ART at any point during the 24 week trial (proportion; self-reported medication adherence measure). *Chi-squared test comparing proportion to treatment assignment, for those prescribed ART.*
- c. **Retention in HIV Care** Number of HIV primary care visits at 24 weeks (count, chart abstraction). *Outcome scores will be analyzed via rank-based methods such as Wilcoxon rank-sum tests.*
- d. **HIV Risk Behaviors** Past 30 day injection drug use, unprotected sex, multiple sexual partners as measured by the RAB at week 24 (binary; self-report). *Chi-squared test comparing proportion to treatment assignment.*
- e. **Quality of life** Past 30 day health-related quality of life as measured by EQ-5D at week 24. *Change from baseline in mean EQ5D score assessed by treatment group using paired t-test, or analysis of change via ordinary least squares.*

[figure not shown]
3) ART Adherence Mediation Variables and Mediation Analysis:

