17.10 ITT and Per-Protocol Analyses, Missing Data and Dropouts

Analysis will be ITT in the sense that participants will be analyzed as being members of the arm to which they were originally randomized. With one exception, we plan in the primary analysis to recode missing data to “unsuppressed” because, in this setting, this seems more realistic than assuming that missingness is non-informative for suppression. The exception is that, if missing data are flanked on both sides by “suppressed” values, we will impute the missing data to be suppressed. Sensitivity analyses will secondarily explore the implications of this MNAR imputation, and outcomes according to treatment received. Per-protocol sensitivity analyses will compare outcomes among those who initiated at least one dose of XR-NTX compared with those who initiated at least one dose of buprenorphine or methadone.

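### The t-tests on 24-week change in VACS Index and CD4 drop participants who died or have no follow-up value, and are biased if informative loss differs between arms

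*Combined protocol and SAP*

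**What the plan says.** Section 17.9, items 1a and 1b, sets the analysis of the two secondary HIV outcomes. Change in VACS Index is taken at week 24 "compared with randomization (score based on lab measurements). T-test". Change in CD4 is taken "at 24 weeks following randomization compared with randomization (count; laboratory measurement). T-test". Neither item says what happens to a participant with no follow-up value.

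The rules for missing data and death sit elsewhere and concern viral suppression. Section 17.2 argues that "if data are missing, it is probably because the participant is unsuppressed", and says that the status of unsuppressed "will be assigned as a status value for visits subsequent to death". Section 17.10 limits the recode in the same way: "we plan in the primary analysis to recode missing data to" unsuppressed. Its one exception, for a gap flanked by suppressed values, cannot apply at week 24, the last viral-load visit.

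Section 17.9.1 adds GEE models for the secondary outcomes. It describes them as a means of covariate adjustment and gives no rule for death or missing laboratory values.

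On data collection, Section 13.5 says "CD4 Count (T-helper cells): will be drawn at randomization and at 12 and 24 week visits or the end of study visit" when that is not week 24. It also schedules HIV RNA, AST and ALT at week 12. Section 11.4 has the VACS Index assessed at randomization and at week 24 or the end-of-study visit, and says that the index "is a potent predictor of mortality in HIV-infected patients".

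**The concern.** The plan takes two views of the same absent participant. Someone with no week-24 blood counts as a failure in the primary analysis and is simply absent from the VACS and CD4 tests, although HIV RNA and CD4 are both components of the VACS Index. A participant who dies counts as unsuppressed in the primary analysis and drops out of the average of a mortality-risk score.

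The t-test then compares survivors with a result, not all randomized participants. If one arm loses more poor responders than the other, its remaining participants look healthier for that reason alone. The secondary biomarkers could then disagree with the primary result without any real difference behind the disagreement.

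**Working it through.** The documents give no power, SD or arm-specific missing rate for either t-test, so there is no figure of theirs to reproduce. The check asks how large the bias could be with no true difference between arms.

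**Inputs from the documents**
- Pilot missing rate for viral load: 6/36 = 17% (Section 9.2.3.3).
- HIV RNA item of the VACS Index: 0 points below 500 copies, 7 from 500 to 100,000, 14 above (Section 11.5, Table 1).
- Meaningful VACS difference: 5 points (Section 11.4).
- Suppression of 57.3% in the observational buprenorphine cohort (Section 17.6).
- 175 per arm and a risk-ratio margin of 0.75 (Section 17.1).

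**Derived input.** A lower suppression rate, 52%, is the rate at which a simple log risk-ratio test has 80% power. The standard error is √(2 × 0.48/(0.52 × 175)) = 0.103, and 0.288/0.103 − 1.96 ≈ 0.84, which gives 80%.

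**Assumed inputs.** Missing rates differ by 10 points: 22% vs 12% (centred on 17%), or 27% vs 17%. All missing participants are unsuppressed, as Section 17.2 supposes is probable.

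**VACS, through the HIV RNA item alone.** Let p be the suppressed share of all randomized, equal in both arms, and m an arm's missing rate. Among those observed, the suppressed share is p/(1 − m). If suppression removes k points, then

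bias = k × [p/(1 − m₁) − p/(1 − m₂)].

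| p | m₁ vs m₂ | Difference in observed suppressed share | k = 7 | k = 14 |
|---|---|---|---|---|
| 0.52 | 22% vs 12% | 0.667 − 0.591 = 0.076 | 0.53 | 1.06 |
| 0.573 | 22% vs 12% | 0.735 − 0.651 = 0.083 | 0.58 | 1.17 |
| 0.52 | 27% vs 17% | 0.712 − 0.627 = 0.086 | 0.60 | 1.20 |
| 0.573 | 27% vs 17% | 0.785 − 0.690 = 0.095 | 0.66 | 1.32 |

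This is 11% (0.53/5) to 26% (1.32/5) of the meaningful difference. With m₁ = m₂ it is zero.

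**Effect on the VACS test.** This simulation had 175 per arm, an assumed SD of 15 points, 50% good responders and a gap of D points in mean change between good and poor responders. Two-sided 5% tests with no true effect rejected as follows:
- 17% loss in each arm, all poor responders, D = 10: 5.0%.
- 25% vs 10% loss, all poor responders, D = 10: 9.0%. The bias is 10 × (0.40/0.90 − 0.25/0.75) = 1.1 points.
- 30% vs 10% loss, all poor responders, D = 14: 20.3%.
- 25% vs 10% loss, 75% of the missing poor responders, D = 10: 5.5%.
- 25% vs 10% loss unrelated to response, D = 10: 4.8%.

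**CD4.** Week-12 and week-24 changes were simulated in SD units with an assumed correlation of 0.7, equal true means and logistic dropout.

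| Dropout depends on | Scenario | Bias of t-test on observed values | Bias left by a model using week 12 |
|---|---|---|---|
| Week-12 response | 22% vs 12% missing, slope 1 in both arms | 0.057 SD | 0.00 |
| Week-12 response | 17% missing in both, slope 1 vs 0 | 0.103 SD | 0.00 |
| Week-24 response | 22% vs 12% missing, slope 1 in both arms | about 0.08 SD | 0.04 to 0.05 SD |
| Week-24 response | 17% missing in both, slope 1 vs 0 | about 0.15 SD | about 0.08 SD |

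Equal missing rates are therefore not enough: the loss must also be of the same kind. The zero in the first two rows follows from letting dropout depend only on week 12. When it depends on the unseen week-24 value, which is closer to the plan's own view, 53% to 56% of the bias remains.

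**The case against.** **Some values are recovered.** The plan never declares a completers' analysis; that is what a plain t-test with no missing-data rule amounts to. An end-of-study visit can stand in for week 24 (Sections 11.4 and 13.5), and participants who withdraw are asked to attend one (Section 23.9). Section 9.1.6 allows chart abstraction up to 52 weeks after randomization, including viral load, CD4, liver enzymes and blood count. Section 9.2.3.3 also expects fewer missing viral loads than the pilot's 17%. All of this stands and narrows the gap. It does not recover participants who died or had no blood drawn, and Section 7.4 rules out study blood draws during incarceration.

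**The GEE models could use week 12.** Section 17.9.1 covers continuous outcomes, so week-12 CD4 might enter. A reader might infer that the plan discards it, but the documents leave the matter open. They do not say that it enters, and a GEE would not by itself deal with death.

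**The VACS range leans high.** Entry requires more than 200 copies, but the RNA item scores 0 below 500, so some participants who become suppressed lose no points. The 14-point case needs every one of them to start above 100,000. That is why 1.3 is an upper bound for this item at these missing rates.

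**Unequal loss is not shown.** A reader might take the pilot's 5 of 12 XR-NTX starts within 4 weeks (Section 4.3) as evidence of unequal missing blood. It is non-initiation: such participants stay in follow-up (Section 9.6) and may start XR-NTX until week 20 (Section 9.1.9).

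**The consequence is limited.** These are secondary outcomes without type I error control (Section 17.9.1). This stands.

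**Conclusion.** The point holds in conditional form. The plan has no rule for death or missing values in its first two secondary outcomes, although its own reasoning for the primary outcome says that such loss is probably informative. If informative loss differs between arms, both comparisons lean toward the arm that loses more poor responders. The size is about 0.5 to 0.7 VACS points through a 7-point RNA item, at most 1.3 through a 14-point one, and about 0.06 to 0.10 SD for CD4 with dropout on week-12 response. These figures rest on assumed missing rates, dropout slopes and a correlation of 0.7. The effect of deaths is not quantified.

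Three stronger readings are not supported. A reader might infer that one arm will look better; with balanced loss of the same kind the bias is zero, and with loss unrelated to response it is essentially zero. A reader might scale the CD4 bias against the coefficient of .164 in Section 17.9; that belongs to the mediation power statement, and the plan sets no CD4 target. A reader might also expect a model using week 12 to remove the bias; it does so only if dropout depends on week-12 response.

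The primary conclusion is unaffected. The change should be made before outcome data are seen, because the trial is open-label and a later choice of method could look selective.

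**What to change.** Amend Section 17.9, items 1a and 1b.

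1. **CD4:** replace the t-test with a likelihood-based repeated-measures model on weeks 0, 12 and 24 in all randomized participants, with arm by visit and the week-24 contrast as the test.
2. **VACS Index:** multiply impute missing week-24 scores among survivors, using the baseline components and the week-12 HIV RNA, CD4, AST and ALT already drawn.
3. **Sensitivity, both outcomes:** steps 1 and 2 assume data missing at random, so add a missing-not-at-random analysis. For VACS, set missing HIV RNA to unsuppressed, in line with Section 17.2. For CD4, use delta-adjusted imputation over a stated range.
4. **Deaths, both outcomes:** add a supportive rank test with deaths ranked worst. This carries over the reasoning of Section 17.2, which holds death at least "as undesirable as lack of suppression, “unsuppressed” will be assigned as a status value for visits subsequent to death".

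State also how end-of-study and chart-abstracted values count as week-24 values.

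The cost is SAP text and a little more programming, with no new visits, blood or participants. The drawback is that the main estimates become model-based rather than simple differences in means.

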5.2 Secondary Objectives

Secondary Specific Aims: Secondary aims compare the effectiveness of XR-NTX versus TAU in 1) other HIV outcomes (VACS Index, CD4 count), 2) engagement in HIV care (receipt of ART, ART adherence, retention in HIV care, HIV risk behaviors), and 3) ART adherence as mediated by number of opioid use days at 24 weeks. An additional secondary aim assesses barriers and facilitators of implementing XR-NTX for retaining patients in HIV primary care.

1) Secondary HIV Outcomes

- a. Change in VACS Index at 24 weeks, compared with randomization.
- b. Change in CD4 count at 24 weeks, compared with randomization.

2) Engagement in HIV Care:

- a. Proportion of participants prescribed ART within 24 weeks following randomization.
- b. Proportion of participants taking 100% of prescribed ART doses in the past month at 24 weeks for those prescribed ART at any point during the 24 week trial.
- c. Retention in HIV Care: Proportion of participants with at least 1 HIV primary care visit in the past 12 weeks, measured at week 24.
- d. HIV Risk Behaviors, as measured by the RAB at week 24.
- e. Quality of life as measured by EQ-5D at week 24, compared to baseline.

3) ART Adherence Mediation Variables:

- a. Number of days of opioid use since baseline, measured by Timeline Follow Back (TLFB) at 24 weeks.
- b. Past 30 day opioid abstinence (by Addiction Severity Index (ASI)-lite self-report, Timeline Follow Back (TLFB) and urine drug screen (UDS) confirmation at 24 weeks).

4) Assess barriers and facilitators of XR-NTX implementation to improve retention in HIV primary care:

Qualitative interviews with participants, providers, and staff to document the HIV primary care treatment environment and describe XR-NTX formative implementation strategies, challenges, and best practices.

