8.2 Secondary Outcome Measures

1) Secondary HIV outcomes:

- a. VACS Index. Change in VACS Index at 24 weeks compared with randomization. (score; derived from screening and week 24 laboratory and demographic data).
- b. CD4 Count. Change in CD4 count at 24 weeks compared with randomization (count; laboratory assay).

2) Engagement in HIV Care:

- a. ART Prescribed. Proportion of participants prescribed ART within 24 weeks following randomization (binary; medical record abstraction).
- b. ART Adherence. Proportion of participants taking 100% of prescribed ART doses in the past month at 24 weeks for those prescribed ART at any point during the 24 week trial (binary; self-reported VAS medication adherence measure).
- c. Retention in HIV Care. Proportion of participants with at least 1 HIV primary care visit in the past 12 weeks, measured at week 24 (binary; medical record abstraction).
- d. HIV Risk Behaviors. Past 30 day injection drug use, unprotected sex, multiple sexual partners as measured by the RAB at week 24 (binary; self-report).
- e. Quality of life. Past 30 day health-related quality of life as measured by EQ-5D at week 24, compared to baseline.

3) ART Adherence Mediation Variables:

- a. Days of Opioid Use. Number of days of opioid use since baseline, as measured by Timeline Follow Back (TLFB) at 24 weeks (count; self-report).
- b. Opioid Abstinence. Past 30 day opioid abstinence (by Addiction Severity Index (ASI)-lite self-report, Time-Line Follow-Back (TLFB) and urine drug screen (UDS) confirmation) in the final 30 days of the 24 week trial (binary; self-report + UDS).

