9.2 Treatment Conditions

9.2.1 HIV Usual Care (Both Arms)

All participants will receive comprehensive HIV primary care, case management, addiction counseling, and social support services from HIV clinics as they would regardless of study participation. As part of protocol training, HIV clinic providers will be encouraged to offer ART within 4 weeks of randomization for participants not already prescribed ART. Current guidelines recommend offering ART to all HIV-infected participants, regardless of CD4 count [35]. The schedule of medical care provided will be as deemed appropriate by the treating provider. HIV-infected participants are typically seen at least twice within the first month of initiating ART, and at least every 3 months thereafter for monitoring. Medical visits will not be considered study visits, though they may coincide with study visits. HIV clinic treatment will also include usual addiction counseling services, which are offered as a part of usual care in most large U.S. HIV clinics. As part of protocol training, HIV clinic providers will be asked to refer study participants to existing addiction counseling services in their clinic, as they would do regardless of study participation. Throughout the course of the trial, HIV clinics will be monitored for any potential changes that might occur in standard practice around medical management of HIV infection or addiction treatment services. Throughout study participation, HIV clinic medical visits will be tracked through medical record abstraction, and counseling visits will be tracked through participant self-report (See Section 10, Assessments).

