11.2 HIV Care Utilization

Study staff will assess the number of HIV primary care visits at baseline and 24 weeks, or the end of study visit, if not week 24 (count, chart abstraction).

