17.3 Secondary Outcome Measures

1) Secondary HIV outcomes variables:

- a. VACS Index. Change in VACS Index score at 24 weeks compared with randomization (continuous; laboratory assays and demographics).
- b. CD4 Count. Change in CD4 count at 24 weeks following treatment initiation compared with randomization (count; laboratory assay).

2) Engagement in HIV Care Variables:

- a. ART prescribed. Proportion of participants prescribed ART within 24 weeks following randomization (binary; medical record abstraction).
- b. ART Adherence. Proportion of participants taking 100% of prescribed ART doses in the past month at 24 weeks for those prescribed ART at any point during the 24 week trial (binary; self-reported medication adherence measure).
- c. Retention in HIV Care: Proportion of participants with at least 1 HIV primary care visit in the past 12 weeks, measured at week 24. Adherence to HIV clinic visits in the year after ART initiation predicts HIV disease progression and death [164] (binary; medical record abstraction).
- d. HIV Risk Behaviors. Past 30 day injection drug use, unprotected sex, multiple sexual partners as measured by the RAB at week 24 (binary; self-report).
- e. Quality of life. Past 30 day health-related quality of life as measured by EQ-5D at week 24.

3) ART Adherence Mediation Variables:

- a. Days of Opioid Use. Number of days of opioid use since baseline, measured by Timeline Followback at 24 weeks (count; self-report).
- b. Opioid Abstinence. Past 30 day opioid abstinence (by Addiction Severity Index (ASI)-lite self-report, Time-Line Follow-Back (TLFB) and urine drug screen (UDS) confirmation) in the final 30 days of the 24 week trial (binary; self-report + UDS).

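### Section 17.9 tests retention as a visit count instead of the binary outcome defined in 5.2, 8.2 and 17.3, and its first-listed EQ-5D test does not compare the arms; the ART-prescription wording also needs reconciling

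*Combined protocol and SAP*

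**What the plan says.** **Aim.** Section 5.2 makes the secondary aims between-arm comparisons: "Secondary aims compare the effectiveness of XR-NTX versus TAU".

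**Rule for analysis.** Section 17.9 opens with "Secondary outcomes will be analyzed as indicated in the italicized text describing each secondary endpoint".

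**Retention.**
- 8.2, item 2c: "Proportion of participants with at least 1 HIV primary care visit in the past 12 weeks, measured at week 24 (binary; medical record abstraction").
- 17.3, item 2c: "Proportion of participants with at least 1 HIV primary care visit in the past 12 weeks, measured at week 24", also labelled binary. Section 5.2 gives the same definition.
- 17.9, item 2c: "Number of HIV primary care visits at 24 weeks (count, chart abstraction"), analysed by rank-based methods such as the Wilcoxon rank-sum test.
- 11.2: "Study staff will assess the number of HIV primary care visits at baseline and 24 weeks", again a count.

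**ART prescription.** Section 17.3, item 2a, has "Proportion of participants prescribed ART within 24 weeks following randomization (binary; medical record abstraction"), and 5.2 and 8.2 agree. Sections 17.9 (item 2a) and 11.1 work with change from baseline. In 17.9 each person is scored 0 or 1 at both times, and the difference is ranked.

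**EQ-5D.** Section 17.9, item 2e, offers a paired t-test of change by treatment group, or ordinary least squares on change. It gives no rule for choosing between them.

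**Supplementary models.** Section 17.9.1 adds covariate-adjusted GEE models on top of the listed tests: a binomial distribution with logit link for binary outcomes, and other suitable forms for continuous or ordinal ones. It states that overall Type I error is not controlled for these analyses.

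**The concern.** An analyst following 17.9 would not test retention as the protocol defines it. The definition asks whether a participant is still attending late in follow-up; the count asks how often the participant attended, with no stated window. The two can give different answers, and the document does not say which prevails. For outcomes without Type I error control, a single prespecified definition is the main protection against choosing a version after seeing the data.

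The EQ-5D problem is of another kind. Two within-arm tests answer whether each arm changed. One significant and one non-significant result is not evidence of a difference between arms, and two significant results are not evidence that there is none.

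**Working it through.** The documents state no power or expected rates for these outcomes, so there is no planned figure to reproduce. The calculations use the planned 175 per arm (17.1), two-sided 5% tests and assumed rates.

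**1. Retention.**

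Binary test, assuming 70% versus 55% with a late visit. The mean proportion is 0.625.
- SE under the null = √(2 × 0.625 × 0.375 / 175) = 0.0518.
- SE under the alternative = √((0.70 × 0.30 + 0.55 × 0.45) / 175) = 0.0511.
- z = (0.15 − 1.96 × 0.0518) / 0.0511 = 0.95, so power is about 83%.

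Count test, by simulation (3,000 trials per scenario). Early visits (weeks 0–12) are negative binomial with shape 1 or 2, either independent of retention or lower in those not retained. Late visits are 0, or 1 plus a negative binomial with mean 0.5 in those retained. Ranges cover these variants.

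| Late visit | Mean early visits | Count test rejects | Binary test rejects |
|---|---|---|---|
| 70% vs 55% | 1.5 vs 1.0 | 89–97% | 82–84% |
| 70% vs 55% | 1.5 vs 1.2 | 67–80% | 82–84% |
| 70% vs 55% | 1.5 vs 1.5 | 24–26% | 82–84% |
| 70% vs 55% | 1.5 vs 1.725 | 6–10% | 82–84% |
| 70% vs 70% | 1.5 vs 2.0 | 30–55% | 5–6% |

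In the fourth row mean totals are equal: 1.5 + 0.70 × 1.5 = 2.55 and 1.725 + 0.55 × 1.5 = 2.55.

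A simpler model shows the same divergence. Let total visits be Poisson with mean 2 in both arms, with 50% versus 30% of visits falling late. The defined outcome is then 1 − e^(−1.0) = 63% versus 1 − e^(−0.6) = 45%. The binary test rejects in 93% of trials and the count test in 5%.

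**2. EQ-5D.** Changes are in SDs of the change score. With the same true change in both arms, let π be the power of the paired test in one arm. The chance that exactly one arm is significant is 2π(1 − π).

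| True change, both arms | π | Exactly one arm significant |
|---|---|---|
| 0.10 | 0.26 | 38% |
| 0.15 | 0.51 | 50% |
| 0.20 | 0.75 | 38% |
| 0.30 | 0.98 | 5% |

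If the true changes are 0.3 and 0.6, both paired tests are significant in 98% of trials (0.977 × 1.00) and do not show the difference. A between-arm t-test has 80% power for it.

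**3. ART prescription.** Let b be the share on ART at baseline (all assumed to stay on), s the share of the rest who start, p = b + (1 − b)s the defined proportion, and c = (1 − b)s the mean change score. Then c = p − b. Randomization makes b equal between arms in expectation, so c₁ − c₀ = p₁ − p₀. The contrast is the same; the variance is not. The ratio of change-score variance to that of the proportion is c(1 − c) / [p(1 − p)]. At b = 0.5:
- s = 0.2: 0.10 × 0.90 / (0.60 × 0.40) = 0.38.
- s = 0.5: 0.25 × 0.75 / (0.75 × 0.25) = 1.00.
- s = 0.8: 0.40 × 0.60 / (0.90 × 0.10) = 2.67.

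Simulated power, change score against proportion, is 75% vs 50% for starting rates of 20 vs 40%, 58% vs 58% for 40 vs 60%, and 49% vs 75% for 60 vs 80%. Neither version is uniformly more precise.

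**The case against.** **Section 17.9.1 fills the gaps.** It promises a binomial model for binary secondary outcomes and suitable models for continuous ones, which would include EQ-5D. The OLS option in item 2e could also carry an arm contrast. This has weight: a reader might infer that the EQ-5D aim would go unanswered, and the documents do not support that. But 17.9.1 supplements the listed tests, does not say which version of retention it models, and, like the OLS option, names no treatment term.

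**Only the method is italicized.** In item 2c the italics cover the rank-based method, not the count. A tie-corrected rank-sum test on a binary variable is practically a chi-squared test, so the method could serve the defined outcome. That is right about the method. The item still names the count as the variable, and 11.2 repeats it.

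**The ART change score tests the wrong thing.** A reader might infer this because someone always on ART and someone never on ART both score 0. The inference fails: the expected arm difference is unchanged, as shown above. What stands is inconsistent wording and a loss or gain of precision whose direction the documents do not settle.

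**The retention illustrations are selective.** The sharpest contrasts need early attendance to be equal between arms or to run against late attendance, and nothing in the documents predicts that. When early attendance strongly favours the retained arm, the count is the more powerful test. This stands as a limit on size. It does not remove the conflict over which outcome is tested.

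**Conclusion.** The point holds for retention and EQ-5D. Retention has two incompatible definitions, 5.2, 8.2 and 17.3 against 11.2 and 17.9, and the listed test follows the one that is not the defined outcome. The first-listed EQ-5D test gives no XR-NTX versus TAU contrast, and nothing obliges the analyst to use the alternative that could. ART prescription is a point of reconciliation only.

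The textual conflict rests on no assumption. Its size does: every rate above is assumed, and the count test can be anywhere from much weaker than the binary test to somewhat stronger. The effect is confined to secondary outcomes without Type I error control; the primary analysis and the sample size are untouched. The change should be made before analysis.

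**What to change.** 1. **Retention.** In 17.9, test the defined binary outcome between arms, by chi-squared as in items 2b and 2d or by the binomial/logit model of 17.9.1. Keep the visit count as supportive and align 11.2.
2. **EQ-5D.** Replace the paired t-test with a regression of week-24 EQ-5D on treatment and baseline EQ-5D, and report the treatment term. Section 14.7 collects both values.
3. **ART prescription.** Use one definition in 5.2, 8.2, 11.1, 17.3 and 17.9, for example the defined binary outcome compared between arms with baseline ART status as a covariate; 11.1 already collects that status. If nearly everyone on ART at baseline counts as prescribed, a logit model with that covariate may not fit, and a comparison stratified by baseline status is safer.
4. **Section 17.9.1.** State that its models use the same outcome definitions.

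**Cost.** Wording and minor reprogramming. Section 9.2.1 already provides that "Throughout study participation, HIV clinic medical visits will be tracked through medical record abstraction", so no new data are needed if visit dates are kept; that should be confirmed. The binary retention outcome ignores visit intensity and can have less power when early and late attendance move together (82–84% against 89–97% in the first row of the retention table), which is the reason to keep the count as supportive.
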